#### Definition of Reversal of Anticoagulation

- Complete reversal is achieved for a treatment group if the mean WBCT is  $\leq 110\%$  of baseline at any post-baseline time point up to and including 1 hour following test

article administration. Complete reversal is achieved for a subject if WBCT is  $\leq 110\%$  of baseline at any post-baseline time point up to and including 1 hour following test article administration

- Complete and sustained reversal of anti-coagulation is achieved for a treatment group if the mean WBCT is  $\leq 115\%$  of baseline at all time points between 1 and 8 hours (inclusive) following test article administration. Complete and sustained reversal of anti-coagulation is achieved for a subject if WBCT is  $\leq 115\%$  of baseline at all time points between 1 and 8 hours (inclusive) following test article administration.

#### Statistically Significant Complete Reversal

- Statistically significant complete reversal, relative to mean placebo WBCT, is defined as  $p < 0.05$ , (one tailed) from the comparison of means between treatment and placebo at 15, 30, 45 minutes or 1 hour post study drug administration as measured by one-way Analysis of Variance (ANOVA) at study completion. Distribution diagnostics will be performed to assure assumptions associated with using ANOVA are met. One-tailed Dunnett's test will be used for comparisons of treatment means.

Analysis of Means (ANOM) methods will also be used to compare means and variances across groups. These methods will be appropriate to test if any of the group means are statistically different from the overall mean or if the group standard deviations are statistically different from the root mean square error (RMSE).

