- Complete reversal is defined as a return of mean WBCT to $\leq 110\%$ of baseline up to and including 1 hour following test article administration.
- Complete and sustained reversal of anti-coagulation is defined as a return of mean WBCT to $\leq 115\%$ of baseline at all time points between 1 and 8 hours following test article administration. Dose escalation or de-escalation will be determined by this criterion.

Details of all statistical analyses will be specified in a separate statistical analysis plan (SAP) that will be finalized prior to data base lock.

Date of Original Protocol:

Prepared in: Microsoft Word 2013

STUDY PROCEDURES:

Day→ Procedure ↓	Screening ^a	Treatment Period					Follow-up
	Day -36 to -1	Day -1 Check-in	Day 1	Day 2	Day 3	Day 4	Day 7-10
Written informed consent	X						
Inclusion/exclusion criteria	X ^b	X					
Demographic data	X						
Height	X						
Weight	X	X					
Medical/ surgical history	X						
Medication history	X						
Physical exam ^{c, d}	X	X					X
Vital signs (BP and HR), RR and temp ^{c, e}	X	X	X	X	X	X	
Safety laboratories ^{c, f}	X	X					X
Fecal occult blood ^f		X					
Drug and alcohol screen ^g	X	X					
Viral hepatitis/HIV serology ^g	X						
12-lead ECG ^{c, h}	X	X	X	X	X	X	
Urine pregnancy test ⁱ	X						X
Serum pregnancy test ⁱ		X					
Admission to CRU ^j		X					
Randomization						X	
Rivaroxaban administration ^k			X	X	X		
Study drug administration ^k						X	
Experimental safety biomarker ^f			X		X		
PD measurements ^{c, l}			X	X	X	X	
PK sample collections ^m			X	X	X	X	
Adverse event monitoring	X	X	X	X	X	X	X
Concomitant medication	X	X	X	X	X	X	X
Discharge from clinical site							X
End of the study participation ⁿ							X

- a. Screening procedures are to be conducted -36 to -1 day before check-in on Day -1. All subjects will be provided lifestyle and dietary guidelines appropriate for an anticoagulant study and for fecal occult blood testing. If the screening visit takes place within 3 weeks prior to check-in, the check-in procedures may be modified to exclude redundant procedures at the discretion of the Investigator.
- b. Subjects should conform to the inclusion/exclusion criteria for the duration of the study. If a subject violates an inclusion or exclusion criterion at any point during the study, he/she may be removed from the study and replaced.
- c. When timing for assessments coincide, PD assessments will be performed first followed by PK assessment(s) and then safety assessments.

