9.7 Pharmacodynamic Analyses

The contract research organization's (██████████) SOPs and Work Instructions will be used as the default methodology if not otherwise specified. All PD computations will be performed using Phoenix® WinNonlin® 6.3, or SAS® Version 9.2 (SAS Institute, Inc., Cary, North Carolina). Graphics will be prepared with SAS® Version 9.2 or SigmaPlot® 12.5. Actual times will be used in the PD analyses.

The PD endpoint will be WBCT.

PD endpoint will be summarized at observed time points and change and/or ratio from baseline values using descriptive statistics and graphical presentations.

Data handling for PD measurements below the limit of quantitation (BLQ) will be specified in the SAP. In the actual analysis, BLQ values will be set to the lower limit of quantitation (LLOQ) for PD data summaries and calculations.

Change-from-baseline and percent-of-baseline will be calculated for all PD endpoints. Baseline for all PD endpoints will be defined as the pre-rivaroxaban sample (approximately four hours before PER977 or placebo administration on Day 3).

The anticoagulant effect of rivaroxaban will be evaluated by comparing WBCT measured at pre-PER977 (about four hours post-rivaroxaban on Day 3) versus baseline (pre-rivaroxaban on Day 3). For the purposes of the PD analyses, subjects with percent-of-baseline WBCT at pre-PER977 $<125\%$ (i.e., $<25\%$ increase) will be considered as rivaroxaban in non-responders and excluded from all PD summaries and assessments.

Listings of individual PD variable collection times, as well as derived sampling time deviations (where applicable), will be provided.

Individual observed and baseline-adjusted values at scheduled time points and PD parameters will be listed and summarized by treatment. In addition, the nature of reversal of anticoagulation (no effect, partial reversal, complete or complete and sustained) based on the definition of reversal of anticoagulation below using WBCT will be listed for each subject and summarized.

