9.8 Analysis of the Primary PD Endpoint (WBCT)

Definition of Reversal of Anticoagulation

- Complete reversal is achieved for a treatment group if the mean WBCT is $\leq 110\%$ of baseline at any post-baseline time point up to and including 1 hour following test article administration. Complete reversal is achieved for a subject if WBCT is $\leq 110\%$ of baseline at any post-baseline time point up to and including 1 hour following test article administration.
- Complete and sustained reversal of anti-coagulation is achieved for a treatment group if the mean WBCT is $\leq 115\%$ of baseline at all time points between 1 and 8 hours (inclusive) following test article administration. Complete and sustained reversal of anti-coagulation is achieved for a subject if WBCT is $\leq 115\%$ of baseline at all time points between 1 and 8 hours (inclusive) following test article administration.

Statistically Significant Complete Reversal

- Statistically significant complete reversal, relative to mean placebo WBCT, is defined as $p < 0.05$, (one tailed) from the comparison of means between treatment and placebo at 15, 30, 45 minutes or 1 hour post study drug administration as measured by one-way Analysis of Variance at study completion. Distribution diagnostics will be performed to assure assumptions associated with using ANOVA are met. Analysis of Means (ANOM) methods will be used to compare means and variances across groups. These methods will be appropriate to test if any of the group means are statistically different from the overall mean or if the group standard deviations are statistically different from the root mean square error (RMSE). Tukey HSD multiple comparison procedure will be used to test for all pairwise differences among the means (Tukey 1953, Kramer 1956). This test is an exact alpha-level test if the sample sizes are the same, and conservative if the sample sizes are different (Hayter 1984).

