### 3.5 Data Handling

Summaries for continuous variables will include the descriptive statistics for number of subjects (n), mean (arithmetic and/or geometric), standard deviation (SD), minimum (min), median, and maximum (max). Summaries for categorical (discrete) variables will include the number of subjects and /or percentage of subjects in a particular category.

Conventions for presentation of numerical data:

Min and max values will be presented to the same number of decimal places as the Electronic case report form (eCRF) data. Means and medians will be presented to one more decimal place than the eCRF data. Standard deviations will be presented to two more decimal places than the eCRF data.

Plasma concentration data will be displayed in listings.

In general, individual and summary values will be displayed as follows:

- (1) Values > 0.0001 and < 1 will be reported to 4 decimal places (e.g., 0.0123).
- (2) Values > 1 and < 10 will be reported to 3 decimal places (e.g., 1.023).
- (3) Values > 10 and < 100 will be reported to 2 decimal places (e.g., 10.23).
- (4) Values > 100 and < 1000 will be reported to 1 decimal place (e.g., 100.2).
- (5) Values > 1000 or equal to 0 will be reported as a whole integer (e.g., 1000).

Values for  $T_{max}$ ,  $t_{last}$  and  $t_{1/2}$  will be reported to 2 decimal places.

All evaluable data from subjects in the analysis sets will be included in the analyses. No adjustment or imputation will be utilized for missing values or for subjects who withdraw

prior to completing the study, neither will analyses be restricted to subjects with complete data. All tabulations will include all placebo subjects pooled across cohorts.

Baseline is defined as the last value measured prior to the first dose of study drug.

Change from Baseline is defined as [Post-baseline Value – Baseline Value].

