## 4.7 Efficacy Analyses

### 4.7.1 Primary Analysis

The efficacy endpoint will be PD assessment of clotting time by WBCT, efficacy endpoint will be summarized at observed time points and change and/or ratio from baseline values using descriptive statistics and graphical presentations. In addition, the summary by time point will include percent-of-baseline  $\leq 110\%$ ,  $\geq 125\%$ , and  $\geq 130\%$ . In addition, an additional summary of the counts and percentages of subjects with  $\leq 110\%$ , and  $\leq 115\%$  at each time point (categorical) will be produced.

Change-from-baseline and percent-of-baseline will be calculated for all efficacy endpoints. Baseline for all efficacy endpoints will be defined as the pre-rivaroxaban sample (approximately 4 hours before ciraparantag or placebo administration on Day 3).

The anticoagulant effect of rivaroxaban will be evaluated by comparing WBCT measured at pre-ciraparantag (about four hours post-rivaroxaban on Day 3) versus baseline (pre-rivaroxaban on Day 3). For the purposes of the efficacy analyses, subjects with percent-of-baseline WBCT at pre-ciraparantag  $< 125\%$  (i.e.,  $< 25\%$  increase) will be considered as rivaroxaban non-responders and excluded from all efficacy summaries and assessments.

Listings of individual efficacy variable collection times, as well as derived sampling time deviations (where applicable), will be provided.

Individual observed and baseline-adjusted values at scheduled time points and efficacy parameters will be listed and summarized by treatment. In addition, the nature of reversal of anticoagulation based on the definition of reversal of anticoagulation below using WBCT will be listed for each subject and summarized.

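### A dose group can be reported as showing statistically significant complete reversal, or complete and sustained reversal, without ever meeting the plan's 110% criterion for complete reversal

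*SAP*

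**What the plan says.** SAP 4.7.1 gives three definitions in sequence.

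1. Complete reversal: "Complete reversal is achieved for a treatment group if the mean WBCT is" at or below 110% of baseline at any time point after study drug up to 1 hour. The same rule applies to a subject's own value.
2. Complete and sustained reversal: the group mean, or the subject's value, is at or below 115% of baseline at every time point from 1 to 8 hours. The subject version opens "Complete and sustained reversal of anti-coagulation is achieved for a subject if WBCT is".
3. Statistically significant complete reversal: "Statistically significant complete reversal, relative to mean placebo WBCT, is defined as" a one-tailed p below 0.05 in a one-way ANOVA, with Dunnett's one-tailed test for the dose means. Protocol 9.8 has the same definition, resting on the "comparison of means between treatment and placebo at 15, 30, 45 minutes or 1 hour post study drug administration", but with Tukey's procedure where the SAP now has Dunnett's.

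Definitions 2 and 3 contain no 110% condition and do not refer back to definition 1. Protocol 9.7 sets out one classification, "the nature of reversal of anticoagulation (no effect, partial reversal, complete or complete and sustained", to be listed for each subject and summarised. SAP 4.7.1 keeps that listing but not the list of categories.

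**The concern.** A comparison with placebo and a return to near baseline are different claims. A dose can lower WBCT clearly below placebo and still leave it well above 110%. As written, such a dose is reported with the words *complete reversal* in its label.

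This label is the SAP's only inferential statement about complete reversal, and it uses the time points that SAP 3.1.1 names for the primary endpoint. Protocol 5.9 says the study is meant to establish a dose that fully reverses steady-state rivaroxaban, so the label bears directly on the main conclusion.

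The second label has a related fault. A subject or group at 113% throughout is *complete and sustained* but never *complete*, so the category listed last in Protocol 9.7 does not contain the one before it. A programmer cannot tell from the text where such a subject belongs.

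**Working it through.** **Design figure.** SAP 3: 16 subjects per cohort, randomised 3:1, up to four cohorts. That is 4 × 12 = 48 active and 4 × 4 = 16 placebo, total 64, which matches the planned number randomised in SAP 3.4. SAP 3.5 says "All tabulations will include all placebo subjects pooled across cohorts"; I take the same pooling to apply to the test. No power or effect size is stated, so there is none to reproduce.

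**Smallest significant difference at one time point.**
- Residual degrees of freedom: 64 − 5 = 59.
- Correlation between dose-versus-placebo contrasts: 12/(12 + 16) = 0.429.
- One-sided 5% Dunnett critical value, four doses, by numerical integration: 2.228. Simulation gives 2.226.
- Standard error factor: √(1/12 + 1/16) = 0.382.
- Required difference: 2.228 × 0.382 = 0.851 SD. Without Dunnett's adjustment it would be 1.671 × 0.382 = 0.638 SD, so the figures below use the stricter reading.

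**Highest dose mean that still earns the significance label.** This is the placebo mean minus 0.851 × SD. The documents give neither SD nor placebo level and do not name the scale of the test. Both inputs are assumptions, in points on the percent-of-baseline scale. A placebo level of 125% is the minimum value for entry before study drug.

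| Placebo mean | SD 10 (needs 8.5) | SD 15 (needs 12.8) | SD 20 (needs 17.0) |
|---|---|---|---|
| 120% | 111.5% | 107.2% | 103.0% |
| 125% | 116.5% | 112.2% | 108.0% |
| 130% | 121.5% | 117.2% | 113.0% |

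The qualifying mean falls to 110% when SD = (placebo − 110)/0.851: 11.8 for placebo at 120%, 17.6 at 125%, 23.5 at 130%. Above those SDs the test is the stricter requirement.

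**How often it would happen.** Simulation at one time point, true means 120% (dose) and 130% (placebo), pooled variance on 59 df. The chance of earning the label is 0.65 at SD 10 and 0.32 at SD 15. The chance of earning it with an observed dose mean at or below 110% is under 0.1% and about 1%. If the true dose mean is 118%, the label is earned with an observed mean above 110% in about 82% of trials at SD 10 and 42% at SD 15. The definition accepts any of four time points, so the chance over the first hour is at least as large if these means persist.

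**The sustained label.** By definition, a constant 113% satisfies 115% at 1, 2, 4, 6 and 8 hours and never satisfies 110%. For a group of 12 with a flat true mean of 113% and an assumed within-subject correlation of 0.5 to 0.8, the chance of *complete and sustained* without *complete* is about 69–78% at SD 5 and 18–31% at SD 10.

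**Check against the sponsor's own data.** Protocol 1.2.4 reports differences from placebo on Day 3 of the second edoxaban study, significant at most time points from 5 minutes to 3 hours, with geometric ratios of 86.52% to 93.70%. A ratio of 93.70% leaves the dose above 110% whenever placebo exceeds 110/0.9370 = 117.4%. For 86.52% the figure is 110/0.8652 = 127.1%. Significance without reaching 110% is therefore plausible.

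**The case against.** The strongest reply is that the significance definition directly follows the 110% definition in the same section, so *statistically significant* may be meant to qualify a dose that is already complete. That may be the intention, but the text gives the p-value as the whole definition and adds no such condition. If that reading is intended, one linking sentence would settle it.

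Second, this is a matter of labels. Group-level complete reversal is a separate result, and SAP 4.7.1 also plans summaries by time point and "an additional summary of the counts and percentages of subjects with" values at or below 110% and 115%. A careful reader would see a mean of 118% for what it is. This stands, and it limits the severity, but the tables do not correct the headline label.

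Third, the size rests on assumed inputs, and the earlier data cut both ways. In the enoxaparin study (Protocol 1.2.3) the placebo maximum averaged 140.63% of baseline. In the second edoxaban study placebo returned to baseline at 1 to 1.5 hours. With placebo at 120% and SD 15 the test already demands 107.2%. This stands: the figures are illustrative.

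Fourth, Protocol 9.7 never says that its categories are nested, and 110% by 1 hour and 115% from 1 to 8 hours are explicit, separate thresholds. That is fair as a reading, but the second name still contains the word *complete* without its criterion.

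Fifth, adding an observed mean of 110% to a test against placebo does not make the test an inference about 110%. That is correct, and the report should say so.

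**Conclusion.** The concern holds and should be fixed. On the text alone, neither label requires the plan's own criterion for complete reversal, and no other section supplies it. Following the plan exactly could therefore produce a wrong statement about which dose reverses rivaroxaban completely.

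The practical size depends on SD and placebo level, neither of which is documented. For placebo at 125% to 130% and SD 10 to 15, dose means of about 112% to 121% would qualify. With a recovered placebo group or a large SD the gap disappears. No estimate, test or p-value changes.

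**What to change.** - **Significance label.** In SAP 4.7.1 and Protocol 9.8, award *statistically significant complete reversal* only if the group mean is at or below 110% of baseline and the Dunnett-adjusted one-tailed p is below 0.05 at the same time point. Call p below 0.05 alone a statistically significant reduction versus placebo. State that the p-value tests superiority to placebo, not attainment of 110%. If only one change is wanted, the renaming is enough.
- **Sustained label, for reporting only.** Either rename the 1 to 8 hour criterion *sustained WBCT at or below 115%*, or report *complete and sustained* only where 110% was also met by 1 hour. Apply the choice to groups and subjects, and align the Protocol synopsis and 9.7.
- **Consistency.** The synopsis says of the 115% criterion, "Dose escalation or de-escalation will be determined by this criterion". Protocol 5.9 assigns the decision to a review group and does not name that criterion. The two places must be reconciled; no dose rule is proposed here.

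The cost is wording, an entry in SAP 4.11 and a few lines of table code, with no new data or tests. The downside is that fewer doses or subjects may qualify for the labels.

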The primary endpoint of efficacy, the effects of the study drug, ciraparantag compared to a placebo on the reversal of anticoagulation induced by rivaroxaban, will be determined. Blood samples (2 ml) for measuring of clotting time by WBCT will be collected at the following time points:

Day 3: pre-rivaroxaban (within 1 hour prior to dosing) and post-rivaroxaban at 3.75 and post-study drug at 0.25, 0.5, 0.75, 1, 2, 4, 6, 8 and 24 hours (hrs). (Only subjects with at least 25% increase of clotting time from pre-rivaroxaban level on day 3 will be randomized). Triplicate WBCT will be done pre-rivaroxaban, post-rivaroxaban at 3.75 hrs and post-study drug at 1 hr, and median WBCT values will be derived and used for analysis in this study.

Secondary endpoints, including the PK characteristics of rivaroxaban and ciraparantag and its primary metabolite, will be assessed. A 4mL blood sample in potassium EDTA will be collected for each PK assessment of rivaroxaban. Rivaroxaban PK time points include:

Day 3: pre-rivaroxaban (within 1 hr prior to dosing), post-rivaroxaban at 3.75, 4.25, 4.5, 4.75, 5, 6, 8, 10, 12, and 28 hrs.

A 3mL blood sample with no additive (i.e. serum sample) will be collected for each PK assessment of ciraparantag and its metabolite. Ciraparantag or placebo is administered 4 hrs after the rivaroxaban dosing on Day 3. Ciraparantag and its metabolite PK time points include:

Day 3: pre-study drug (within 1 hr prior to dosing of ciraparantag or placebo), post-study drug at 0.25, 0.5, 0.75, 1, 2, 4, 6, 8 and 24 hrs.

Safety monitoring, including medical history interviews, AEs, physical examinations, vital signs, laboratory testing and electrocardiogram (ECG) will be performed.

The schedule of procedures is presented in [Table 1](#). For a detailed description of study procedures, please refer to protocol Section “STUDY PROCEDURES”.

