#### **3.1.1 Efficacy Endpoints**

The primary efficacy endpoint will be the PD assessment of clotting time by WBCT, and clotting time between placebo and treatment at 15, 30, 45 minutes or 1 hour post ciraparantag administration, on Day 3. The PD parameters will include  $E_{min}$ ,  $tE_{min}$ ,  $E_{min(0-6h)}$ ,  $tE_{min(0-6h)}$ ,  $E_{max}$ ,  $tE_{max}$ , and  $\Delta E_{max}$ .

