### **3.3 Randomization**

The Investigator will identify all subjects who meet all inclusion/exclusion criteria and who will be enrolled in the study. Subjects will be enrolled in cohorts of 16 subjects each and will be sequentially assigned Randomization Numbers 1001 to 1016 prior to dosing of study drug on Day 3, after confirmation of eligibility. The next 16 such subjects will be enrolled in Cohort 2, and will be sequentially assigned Randomization Numbers 2001 to 2016. This method of assignment will continue through all four cohorts. Replacement subjects, if applicable will be assigned the same treatment, using the number of the withdrawing subject +100 (e.g. if subject 1001 withdraws, the replacement subject would be 1101).

The assignment of treatment will be based on randomization schedules to be generated prior to study initiation by a statistical programmer at [REDACTED]  
Each cohort will have a different, independently generated randomization schedule.

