#### **4.11 Changes from Pre-Specified Analyses**

The definition of concomitant medication is changed from “any medication other than the trial product that is taken during the trial including the screening period” in the protocol to “any medication other than the trial product that is taken on or after the first dose of rivaroxaban” in the analysis planned for this study.

In the statistical analysis of complete reversal, Tukey HSD multiple comparison procedure was replaced by one-tailed Dunnett’s test for comparison of treatment and placebo means.

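### The significance criterion for complete reversal can be met at any of four time points, but Dunnett's test adjusts only across doses at one; the SAP needs a rule for time

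*SAP*

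**What the plan says.** The primary analysis in SAP 4.7.1 has two parts. The first is descriptive: a treatment group has complete reversal if its mean WBCT is at or below 110% "of baseline at any post-baseline time point up to and including 1 hour following test" article administration.

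The second is inferential. Statistically significant complete reversal is a one-tailed p<0.05 "from the comparison of means between treatment and placebo at 15, 30, 45 minutes or 1 hour post study drug administration", from a one-way ANOVA at study completion with one-tailed Dunnett comparisons. Protocol 9.8 has the same list of times: "one tailed) from the comparison of means between treatment and placebo at 15, 30, 45 minutes or 1 hour post study drug administration". SAP 3.1.1 repeats it in the primary efficacy endpoint: "clotting time between placebo and treatment at 15, 30, 45 minutes or 1 hour post ciraparantag administration".

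SAP 4.11 records the choice of multiplicity procedure, "Tukey HSD multiple comparison procedure was replaced by one-tailed" Dunnett's test, and describes it as a comparison of treatment and placebo means. It does not mention time points. ANOM, also planned, compares groups with the overall mean.

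Neither document names a primary time point, a testing order, a repeated-measures model or an adjustment across the four times. The inferential paragraph does not say whether the 110% criterion must hold as well.

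**The concern.** A one-way ANOVA has treatment group as its only factor, so each time point has its own model. Dunnett's test then holds the any-dose error at 5% within that model only. If the claim may rest on whichever of four models gives p<0.05, there are 4 doses × 4 times = 16 chances and the adjustment covers 4 of them.

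This is the named significance criterion for the primary objective. The sponsor revisited multiplicity for this analysis when it moved from Tukey to Dunnett, so a reader of the report will take a Dunnett p<0.05 as controlled. At stake is the reported conclusion that some dose reverses rivaroxaban. The dosing steps are not at stake: the protocol synopsis ties escalation to the descriptive 115% criterion.

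**Working it through.** **Inputs from the documents.** Four doses (30, 60, 120, 180 mg; SAP 2.2). Sixteen subjects per cohort, 3:1 (SAP 3.4), so 12 per dose and 4 placebo per cohort. Placebo is pooled, 4 × 4 = 16: "All tabulations will include all placebo subjects pooled across cohorts" (SAP 3.5, stated for tabulations and assumed here for the ANOVA). One-tailed 0.05. Four time points.

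**Assumptions.** Normal data, equal variances, equal correlation ρ between any two of the four times. The documents give no ρ, so 0.3 to 0.9 is shown.

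**Step 1, one time point.** Error df = 64 − 5 = 59. The correlation between two dose-versus-placebo contrasts is 12/(12+16) = 12/28. The one-sided 5% Dunnett critical value for four such contrasts is 2.23, against 1.67 unadjusted. In simulation with all doses inert, the any-dose error is 5.0%, which reproduces the plan's 0.05. For one given dose it is 1.5%.

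**Step 2, any of four time points.** The same critical value is applied at each time, and a claim is made if any t exceeds it. With four independent times the rate would be 1 − 0.95⁴ = 18.5%. Simulated rates of at least one false claim are:

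| Inert doses | ρ = 0.3 | 0.5 | 0.7 | 0.9 |
|---|---|---|---|---|
| 4 | 16.9% | 15.2% | 12.8% | 9.3% |
| 3 | 13.6% | 12.3% | 10.3% | 7.5% |
| 2 | 9.8% | 8.9% | 7.5% | 5.4% |
| 1 | 5.4% | 4.9% | 4.1% | 2.9% |

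First-order autoregressive correlation of 0.7 or 0.9 gives 14.1% or 10.2% with four inert doses, so the pattern does not depend on the equal-correlation form.

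**Step 3, if the group mean must also be at or below 110% at the same time.** The four-inert rate now depends on the unreversed mean and the SD. The documents give neither for rivaroxaban. Assuming the comparison is on percent of baseline, SD 8–12 points and ρ 0.9–0.3:

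| Unreversed mean, 15 min to 1 h | Error |
|---|---|
| Flat 110% | 9–17% |
| Flat 115% | 4–14% |
| Flat 120% | 0–2% |
| Flat 125% | about 0% |
| Falling 125% to 115% | 2–5% |
| Falling 125% to 100% | 7–12% |

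**Step 4, Bonferroni over time.** 0.05/4 = 0.0125 per time point. The Dunnett critical value becomes 2.80, and the any-dose, any-time error with four inert doses is 4.7% at ρ = 0.3 and 2.6% at ρ = 0.9.

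**The case against.** **The 110% criterion may be meant to apply too.** The inferential paragraph follows the 110% definition and its title includes the words complete reversal, so significance may be an addition to that criterion and not a substitute for it. Subjects are dosed only if WBCT is at least 125% of baseline at 3.75 hours. If placebo stays near that level for the next hour, the joint rule leaves almost no false claims. This stands as a real possibility. The documents point both ways: with enoxaparin no placebo subject met the 120% criterion through 1–6 hours (protocol 1.2.3), while with edoxaban placebo returned to baseline at 1 hour on one day and 1.5 hours on the other (protocol 1.2.4).

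**Four inert doses is not the expected case.** Earlier edoxaban and enoxaparin studies suggest activity from 60 mg, and the study seeks a reversal dose, a higher dose and at least one partial or no-effect dose. With one inert dose the error is 2.9–5.4%. With none, no claim against placebo is false. This also stands.

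**The four times may be meant as four separate results.** Each Dunnett result is then valid for its own time. The text does not say so, and the any-time wording of the 110% definition favours the other reading. If separate results are intended, no any-time claim should be made.

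**This is exploratory Phase 2 work.** No sample size was calculated and no family-wise rate is stated, so 5% over all doses and times is a benchmark brought to the plan. But the plan attaches a named significance claim to its primary objective, and the claim needs a defined error rate.

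**Conclusion.** The gap is certain: the plan gives no rule for combining four time points, and its multiplicity adjustment covers doses only. Under the reading that p<0.05 at any time suffices, the any-dose false-claim rate is about 9–17% with four inert doses, 5–10% with two and 3–5% with one, for ρ from 0.9 to 0.3. The single-time-point rates are 5% with four inert doses and 1.5% with one.

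A reader might infer that the trial's primary analysis has a false-positive rate two to three times its nominal level. The documents do not support that as a general statement. It needs both the p-value-alone reading and four inert doses. For a claim about one given dose the rate stays near or below 5%. If the 110% criterion must also hold, the rate cannot be determined and may be below 5%.

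The point is worth correcting because the SAP leaves the reader unable to tell which of these rates applies.

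**What to change.** In SAP 4.7.1, keep the ANOVA and Dunnett's test and adopt one of two rules:

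- **(a)** Name one primary time point, or the mean of the four times. Test it with one-tailed Dunnett at 0.05 and report the other times descriptively. One hour is a natural candidate, being the only post-dose time with replicate measurement: "Triplicate WBCT will be done pre-rivaroxaban, post-rivaroxaban at 3.75 hrs and post-study drug at 1 hr".
- **(b)** Keep the any-time rule and run one-tailed Dunnett at 0.0125 per time point (critical value about 2.80). This is conservative when the times are highly correlated.

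In either case, state that the 110% group-mean criterion must be met at the same time point as the significant p-value, or that it is not required. Align SAP 3.1.1 with the choice.

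The change is wording and a threshold; no new data are needed. The cost is power. For a true effect of 1 SD at all four times and ρ from 0.9 to 0.3, the chance of a claim for a given dose is:

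| Rule | Power |
|---|---|
| As written, p-value alone | 77–95% |
| One named time | 65% |
| Mean of the four times | 69–94% |
| Dunnett at 0.0125 per time | 57–81% |

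A named time or a mean loses more if the effect is confined to other times.

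A joint max-t permutation test, permuting within cohort because "Each cohort will have a different, independently generated randomization schedule" (SAP 3.3), would also control the error. It is not recommended as the default: with three doses active at 1 SD and one inert, its power is about 57–73% per active dose, and it replaces the planned method.
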